#### Patients with tumors who respond to treatment will continue until the following:

- Confirmed progression occurs (upon agreement with the ION and Alkermes Medical Monitors, patients tolerating therapy and receiving clinical benefit may be allowed to stay on study for up to 1 year)
- Until unacceptable toxicity occurs
- Other criteria for discontinuation occur

[figure not shown]
Safety and tolerability will be assessed and reported using standard Common Terminology Criteria for Adverse Events (CTCAE) v5.0 criteria. Safety will be monitored by the study Principal Investigator (PI), participating site PIs, the ION Coordinating Center PI and staff, and representatives from Alkermes. Details pertaining to the Safety Review Committee (SRC), including participants, frequency of meetings, and criteria that would trigger ad hoc meetings, are described in the SRC Charter.

If the unacceptable AEs (defined in Section 12.2) observed are typical of known pembrolizumab and/or ALKS 4230 toxicities, the following will be considered: (1) revising the protocol eligibility requirements to decrease the likelihood of toxicities, (2) modifying the dose or schedule, or (3) allowing the study to proceed as designed assuming that patients in this study will have fatal diseases and few other treatment options. The risk/benefit ratio will need to be evaluated in this situation.

If unexpected, unacceptable AEs are considered to be related to concurrent administration of ALKS 4230 and pembrolizumab, the PI, participating site PIs, the ION Coordinating Center PI and staff, and representatives from Alkermes will consider revising the protocol eligibility requirements to decrease the likelihood of toxicities or may consider allowing the study to proceed as designed given the risk/benefit ratio for this population.

Study design schematics are provided in Figure 1 and Figure 2.

#### Figure 1: Study Design Schematic 1

[figure not shown]

Pembrolizumab regimen: 200 mg once Q3W by IV infusion

ALKS 4230 regimen:  $3 \mu g/kg$ , given daily on 5 consecutive days on Days 1 through 5 of the first week of each 3-week treatment cycle.

Abbreviations: CR=complete remission; HNSCC=squamous cell carcinoma of the head and neck; PD=progressive disease; PD-(L)1=programmed cell death ligand-1; PR=partial response; SD=stable disease; Q3W=every 3 weeks

Abbreviations: IV=intravenous; Q3W=every 3 weeks.

## 8.2. Schedule of Assessments

The schedule of assessments for treatment and post-treatment follow-up is shown in Table 4. The schedule of assessments for long-term follow-up is shown in Table 5.

Premature discontinuation procedures are provided in Section 7.3.

Treatment Cycle a				e 1	C	ycle	2	Cycle 3			(	Cycle	4	(	Cycle	5	(Re	bsequ Cycle epeat to 1 y	for		Post-treatment Follow-up		
Weeks	Scree ning	w 1	w 2	w 3	w 4	w 5	w 6	w 7	w 8	w 9	w 10	w 11	w 12	w 13	w 14	w 15	w 16	w 17	w 18	End of Tx a	Safety FU	Disease Assess- ment b	Survi -val FU c
Scheduling window (days) d	-28 to -1 days				-1/ +3			-1/ +3			-1/ +3			-1/ +3			-1/ +3			At time of D/C	30 days ±5 post D/C	Every 8 weeks post D/C for up to 2 years	Every 12 week s for up to 2 years
Pembrolizu- mab		Р			Р			Р			Р			Р			Р						
ALKS 4230		Α			Α			А			Α			Α			Α						
Antipyretics		Х			Х			Х			Х			Х			Х						
										Adn	ninist	rative	Proc	edure	es								
Informed Consent	X e																						
Inclusion/ Exclusion Criteria	X																						
Demographics	X																						
Medical History	X																						
Prior and Concomitant Medications f	X	X			X			X			X			X			X				X		

# Table 4:Schedule of Assessments and Study Visits

Treatment Cycle a		Cycle 1			Cycle 2			Cycle 3			(	Cycle	4	Cycle 5			Subsequent Cycle (Repeat for up to 1 year)				Post-treatment Follow-up		
Weeks	Scree ning	w 1	w 2	w 3	w 4	w 5	w 6	w 7	w 8	w 9	w 10	w 11	w 12	w 13	w 14	w 15	w 16	w 17	w 18	End of Tx a	Safety FU	Disease Assess- ment b	Survi -val FU c
									Cli	nical	Proc	edure	es/Ass	essm	ents								
Review AEs g	Х	Х	Х	Χ	X			Х			Х			Х			Х				X h	X h	
Full Physical Examination	Х																			Х			
Directed Physical Examination		x			X			X			X			X			X						
Vital Signs, Weight, and Height i	X	х			X			Х			X			Х			Х			X			
ECOG Performance Status j	Xj	x			X			Х			X			X			X			Х			
12-lead ECG k	Х	Х																		Х			
	1		1					L	abor	ator	y Ass	essme	ents (S	Safety	Labs	5)						I	1
HBsAg, anti- HCV, and HIV	Х																						
Pregnancy Test – Urine or Serum β-hCG 	Х	X			X			Х			Х			X			Х			Х			
PT/INR and aPTT m	X j					X																	

# Table 4: Schedule of Assessments and Study Visits (Continued)

Treatment Cycle a		0	ycle	ycle 1		Cycle 2			Cycle 3			Cycle	4	Cycle 5			Subsequent Cycle (Repeat for up to 1 year)				Post-treatment Follow-up		
Weeks	Scree ning	w 1	w 2	w 3	w 4	w 5	w 6	w 7	w 8	w 9	w 10	w 11	w 12	w 13	w 14	w 15	w 16	w 17	w 18	End of Tx a	Safety FU	Disease Assess- ment b	Survi -val FU c
	Laboratory Assessments (Safety Labs) (Continued)																						
CBC with Differential n	Xj	x			Х			х			Х			Х			Х			Х	Xº		
Complete Serum Chemistry Panel n	X j	X			X			X			X			X			X			Х	Xº		
Urinalysis n	Xj	X			Х			Х			X p						Х				X°		
TSH, Cortisol, and ACTH q	Х							х						Х			Х						
	•					•				Eff	icacy	Meas	surem	ents		•							
Tumor Imaging	X r						X s				X s						X s			X b,t		X b	
				•		Tu	mor	Biop	sies/	Arcl	nival '	Fissue	e and	Micr	obiota	a Coll	ectior	1					
Archival or Newly Obtained Tumor Biopsy (for Tumor T-cell Clonality; GEP studies, and Sequencing and TMB analysis)		Xu	X v																				

# Table 4: Schedule of Assessments and Study Visits (Continued)

Treatment Cycle a		Cycle 1			C	ycle	2	Cycle 3			(	Cycle	4	Cycle 5			Subsequent Cycle (Repeat for up to 1 year)				Post-treatment Follow-up		
Weeks	Scree ning	w 1	w 2	w 3	w 4	w 5	w 6	w 7	w 8	w 9	w 10	w 11	w 12	w 13	w 14	w 15	w 16	w 17	w 18	End of Tx a	Safety FU	Disease Assess- ment b	Survi -val FU c
					Tum	or B	liops	ies/A	rchiv	al T	issue	and N	Aicro	biota	Colle	ction	(Con	tinueo	1 )				
Stool Sample w		Х				Х																	
	•								Cor	relat	tive S	tudies	s Bloo	d Dra	aws x								•
Immuno- genicity of ALKS 4230		x			X			X			X			X			X				X (14 days post D/C)		
Immuno- phenotyping of PBMC		X	X	X	x	X		Х			Х			Х			Х			Х			
T- and NK-cell Function Analysis		x	X	x	x	x		X			X			Х			Х			Х			
Plasma Cytokine Assays		x			x																		
Kyn/Trp Ratio, Arginine		X			X			Х			Х			Х			Х			Х			

#### Table 4: Schedule of Assessments and Study Visits (Continued)

Abbreviations: A=ALKS 4230: 3 µg/kg, daily for 5 consecutive days on Days 1 through 5 of the first week of each 3-week treatment cycle.

ACTH=adrenocorticotropic hormone; AE=adverse event; aPTT=activated partial thromboplastin time; C=Cycle; CBC=complete blood count; CIML=Central Immune Monitoring Laboratory; CTCAE=Common Terminology Criteria for Adverse Events; D=Day; D/C=discontinuation; ECG=electrocardiogram; ECI=events of clinical interest; ECOG=Eastern Cooperative Oncology Group; FNA=fine needle aspiration; FU=follow-up; GEP=gene expression profiling; HBsAg=hepatitis B surface antigen; hCG=human chorionic gonadotropin; HCV=hepatitis C virus; HIV=human immunodeficiency virus; HPV=human papillomavirus; ID=identification; INR=international normalized ratio; Kyn=kynurenine; NCI=National Cancer Institute; NK=natural killer; P=Pembrolizumab: 200 mg flat dose, once Q3W, starting Cycle 1, Day 1 for up to 1 year; PD=progressive disease; PD-L1=programmed death ligand-1;

#### Protocol ION-01-ALKS4230

PBMC=peripheral blood mononuclear cell; PT=prothrombin time; Q3W=every 3 weeks; RECIST=Response Evaluation Criteria in Solid Tumors; SAE=serious adverse event; TMB=tumor mutational burden; Trp=tryptophan; TSH=thyroid-stimulating hormone; Tx=treatment; w=Week (visit).

- a In general, assessments/procedures are to be performed on Day 1 and prior to the first dose of treatment for each cycle unless otherwise specified. Treatment cycles are 3 weeks; however, the treatment cycle interval may be increased due to toxicity according to the dose modification guidelines provided in Section 9.1.1 and Section 9.1.2.
- b In patients who discontinue study therapy, every effort should be made to continue monitoring their disease status by radiologic imaging per local standard of care or Investigator clinical judgment every 8 weeks for up to 2 years until (1) the initiation of new therapy, (2) death, or (3) the end of the study, whichever occurs first.
- c After the start of new anticancer treatment or documented disease progression by local imaging review, the patient should be contacted by telephone every 12 weeks ( $\pm 1$  week) to assess for survival status for up to 2 years.
- d In general, the window for each visit is -1/+3 days unless otherwise noted. Pembrolizumab is given on Day 1 of each cycle with a -1/+3-day window. ALKS 4230 is given daily on 5 consecutive days on Days 1 through 5 of the first week of each 3-week treatment cycle. Day 1 of each 5-day dosing period will have a -1/+3-day scheduling window; however, all subsequent days within a cycle (Days 2 to 5) must be administered on their scheduled day. Refer to Section 9.5.2 for management of skipped dosing days.
- e Written consent must be obtained prior to performing any protocol-specified procedure. Consent should include option to copy relevant imaging for central review by the manufacturer, enabling confirmation of Investigator-determined responses. Results of a test performed prior to the patient signing consent as part of routine clinical management are acceptable in lieu of a screening test if performed within the specified time frame (eg, within 28 days prior to the first dose of study drug). A patient ID number will be assigned when the patient is enrolled.
- f Prior medications Record all medications taken within 30 days of Screening Visit. Concomitant medications Enter new medications started within 28 days before the first dose of study drug through the Safety Follow-up Visit. Record all medications taken for AEs.
- g AEs and laboratory safety measurements will be graded per NCI CTCAE v5.0. All AEs, whether gradable by CTCAE or not, will also be evaluated for seriousness. The Week 3 AE review can be captured via telephone; no visit is required.
- h Record all AEs occurring within 30 days after the last dose of study drug. Report all SAEs (related and unrelated to study drug) and ECIs occurring up until 90 days after the last dose of study drug or 30 days after the start of new anticancer treatment, whichever comes first. Afterwards, report only SAEs and ECIs that are related to study drug.
- i Vital signs include temperature, pulse, respiratory rate, weight, and blood pressure. Height will be measured at Visit 1 only.
- j ECOG Performance Status and laboratory tests for screening are to be performed within 10 days prior to the first dose of study drug.
- k ECGs should be performed on Day 1, Day 3, and Day 5 of each cycle. ECGs should be performed in triplicate approximately 5 minutes apart at each time point assessed. ECGs will be obtained predose of pembrolizumab on Cycle 2 Day 1. ECGs should also be obtained predose of ALKS 4230, at the end of infusion, and 1 hour (±15 minutes) after the completion of administration of ALKS 4230.
-  A pregnancy test (urine or serum) must be given to all women of childbearing potential before each treatment cycle begins. Pregnancy test results must be confirmed as negative before Dose 1 of each cycle is administered for all cycles.
- m Coagulation factors (PT/INR and aPTT) should be tested as part of the screening procedures and before collection of the post-treatment (second) biopsy for all patients. Any patient receiving anticoagulant therapy should have coagulation factors monitored closely throughout the study.
- n After Cycle 1, laboratory samples can be collected up to 72 hours prior to Day 1 (CBC with differential; complete serum chemistry panel, including magnesium, calcium, and phosphorus; and urinalysis). CBC and complete serum chemistry panel should also be done up to 72 hours prior to Day 1 of the ALKS 4230 infusion.
- o Unresolved abnormal laboratories that are drug-related AEs should be followed until resolution. Laboratories do not need to be repeated after the end of treatment if laboratories are within normal range.

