#### 8.3.15. Adverse Event Monitoring

Adverse events will be monitored continuously from the time a patient signs the informed consent document until the completion of the Safety Follow-up Visit or final disease assessment visit during the post-treatment follow-up (Table 4). Adverse events and serious adverse events (SAEs) are defined in Sections 12.1 and 12.2, respectively. Section 9.5.2 provides stopping criteria, and Section 12.4 provides guidance on the monitoring and recording requirements for AEs. Section 12.5 provides guidance on the reporting requirements for SAEs.

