## 12.4. Monitoring and Recording of Adverse Events

Adverse event data collection will begin after a patient signs the ICF and will continue until completion of the Safety Follow-up Visit for the main part of the study. Long-term collection of AE data is described in Table 5. Any AE or SAE having an onset after the Safety Follow-up Visit will not be collected or reported unless the Investigator feels that the event may be related to the study drug.

The Week 3 AE review can be captured via telephone; no visit is required.

Patients will be instructed by the Investigator or designee to report the occurrence of any AE. All volunteered, elicited, and observed AEs are to be recorded on the AE eCRFs.

The Investigator will assess all AEs regarding any causal relationship to the study drug(s) (see Section 12.3), the intensity (severity) of the event, action taken, and patient outcome. For AEs not clearly related to either ALKS 4230 or pembrolizumab individually, the most conservative approach to treating the event should be used.

The following criteria should be used to guide the assessment of intensity (severity):

- Mild: Causes awareness of sign or symptom, but is easily tolerated; does not interfere with usual activities
- Moderate: Causes discomfort enough to interfere with usual activities
- Severe: Is incapacitating; results in inability to work or perform usual activities

All AEs will be followed until resolution, until deemed stable by the Investigator, or until the patient is deemed by the Investigator to be lost to follow-up.

Immune-mediated AEs will be documented as such using the immune-mediated AE eCRF.

For clinical study safety reporting purposes, the most recent version of the ALKS 4230 IB and the Keytruda USPI will be used as the reference document to designate event expectedness.

Withdrawal from the study as a result of an AE, and any therapeutic measures that are taken, shall be at the discretion of the Investigator. If a patient withdraws from the study for any reason, any ongoing AEs will be followed until resolution, until deemed stable by the Investigator, or until the patient is deemed by the Investigator to be lost to follow-up.

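### Section 12.4 bars unrelated SAEs and ECIs that start after the Safety Follow-up Visit, while Table 4 footnote h and three other parts of the protocol call for them to day 90 or beyond

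*Protocol*

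**What the plan says.** Six places in the protocol bear on events that start after treatment ends.

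- **Section 8.2, Table 4 footnote h**, attached to the AE reviews at the safety and disease-assessment follow-up visits: "Record all AEs occurring within 30 days after the last dose of study drug". Next, "Report all SAEs (related and unrelated to study drug) and ECIs occurring up until 90 days after the last dose of study drug", or until 30 days after new anticancer treatment starts if that comes first. Finally, "Afterwards, report only SAEs and ECIs that are related to study drug".
- **Section 12.4**: for the main part of the study, collection runs from consent to the Safety Follow-up Visit. Then "Long-term collection of AE data is described in Table 5". The next sentence reads "Any AE or SAE having an onset after the Safety Follow-up Visit will not be collected or reported", with a single exception for events that the site physician thinks could be drug-related.
- **Section 8.2, Table 5**: all four patient groups have the same AE-tracking entry, 90 days after discontinuation or 30 days after it if new anticancer therapy begins. There is no limit by seriousness or causality.
- **Section 12.1.1**: ECIs are reportable regardless of causality to 90 days after treatment stops, or 30 days after it stops if new therapy begins.
- **Section 12.5**: all SAEs are reportable within 24 hours of discovery, with no causality condition and no end date. Section 12.5.1 exempts events that indicate disease progression.
- **Section 8.3.15**: monitoring runs "until the completion of the Safety Follow-up Visit or final disease assessment visit during the post-treatment follow-up". It adds that "Section 12.4 provides guidance on the monitoring and recording requirements for AEs" and sends the reader to 12.5 for SAE reporting.

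Table 4 schedules the Safety Follow-up Visit 30 days ±5 after discontinuation. Table 5 adds a second visit of that name, at 90 days, only for patients who progress on study before 1 year.

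SAP 3.13.2 ends the main TEAE analyses 30 days after discontinuation and summarizes later treatment-related AEs separately. SAP 3.13.3 lists deaths from any cause and deaths due to an AE.

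**The concern.** The last sentence quoted from 12.4 is a prohibition, not a minimum that a site may exceed. For an unrelated SAE on day 50, a site cannot obey both that sentence and footnote h. What is at stake is consistent SAE and ECI reporting across sites and, if such an event is fatal, whether the death appears in the SAP 3.13.3 listing of deaths due to an AE.

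A smaller question concerns late related events. Sections 9.5.4.2 and 12.3.1 warn that immune-related events can begin months after the last dose. The only ECI listed in 12.1.1 is a combination of liver tests, so a late, non-serious endocrine or skin event would be neither an SAE nor an ECI. Footnote h does not say what to do with it after day 30.

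**Working it through.** The plan states no figure to reproduce. The check is a comparison of the rules, followed by simple day counts.

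**Rules side by side**, for an event that starts after the 30-day visit and by day 90, with no new therapy:

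| Event | Footnote h | 12.1.1 | 12.5 | Table 5 | 12.4 sentence |
|---|---|---|---|---|---|
| Unrelated SAE | report | only if an ECI | report | track | barred |
| Unrelated non-serious ECI | report | report | not covered | track | barred |
| Related SAE or ECI | report | report if an ECI | report if an SAE | track | collect |
| Related, neither SAE nor ECI | silent | not covered | not covered | track | collect |
| Unrelated, neither SAE nor ECI | silent | not covered | not covered | track | barred |

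The first two rows are the contradiction. In the fourth row footnote h is silent and 12.4 fills the gap, so a site can comply with both.

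**Length of the contradiction.** Assume that discontinuation and last dose coincide at day 0. The span is 90 minus the day of the visit:

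- visit on day 25: 90 − 25 = 65 days
- visit on day 30: 90 − 30 = 60 days
- visit on day 35: 90 − 35 = 55 days

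If new therapy starts on day *t*, with *t* between 30 and 60, footnote h ends at *t* + 30. With the visit on day 30 the span is then (*t* + 30) − 30 = *t* days, for example 45 days when *t* = 45.

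**New-therapy anchor.** Footnote h counts 30 days from the start of new treatment and so ends at min(90, *t* + 30). Table 5 and 12.1.1 count 30 days from stopping study treatment. Applied prospectively, they end at max(30, *t*).

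| *t* | Footnote h ends | Table 5 and 12.1.1 end | Difference (days) |
|---|---|---|---|
| 10 | 40 | 30 | 10 |
| 30 | 60 | 30 | 30 |
| 60 | 90 | 60 | 30 |
| 80 | 90 | 80 | 10 |
| 90 | 90 | 90 | 0 |

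The mismatch is at most 30 days and matters only for unrelated SAEs and ECIs.

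**Secondary point.** Table 5 runs 90 − 30 = 60 days past footnote h's all-AE window. Section 12.4 has no end date for possibly related events.

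**Outputs.** The main TEAE tables stop at 30 days, so they are unaffected when the visit is on day 30. A visit on day 25 would leave 30 − 25 = 5 days in which the 12.4 sentence bars unrelated AEs that footnote h records. Table 5 also lets two groups have the visit before new therapy starts, which could widen that margin for them. The primary endpoint is based on imaging and does not depend on AE collection.

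**The case against.** The strongest reply is that the protocol, read as a whole, already requires these reports. Section 8.3.15 names 12.5, not 12.4, for SAE reporting, and 12.5 requires every SAE without a causality test. Section 12.4 limits its own window to the main part of the study and hands long-term collection to Table 5, which tracks events of any causality to day 90. A sensible site would therefore report.

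Most of this stands as an argument about likely practice, and it limits the harm. It does not remove the contradiction. The sentence after the Table 5 pointer bars unrelated events that Table 5 tracks, so 12.4 conflicts with its own cross-reference. Nor can the 90-day visit be what 12.4 means for everyone, because three of the four Table 5 groups have no such visit.

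The reply is right about footnote h: silence there is not a conflict. A reader might infer that footnote h forbids recording late, non-serious related events, and that the SAP 3.13.2 summary beyond 30 days would be empty. The documents do not support that. Section 12.4 collects any event that may be related, and related SAEs and ECIs remain reportable under footnote h itself. The most that can be said is that a site working from footnote h alone could under-record the rest.

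**Conclusion.** Wrong as written, and minor. Section 12.4 contradicts footnote h, 12.1.1, 12.5 and Table 5 on unrelated SAEs or ECIs that start after the Safety Follow-up Visit. The span is about 60 days (55 to 65) if discontinuation equals last dose and no new therapy starts. For patients who progress before 1 year it disappears if 12.4 means their 90-day visit; the text does not say which visit is meant.

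A reader might infer that unrelated SAEs will be lost across the trial. That goes too far: the other four provisions point towards reporting, so the risk exists only where a site applies the 12.4 sentence literally. The exposed outputs are SAE and ECI safety reporting and possibly the listing of deaths due to an AE. The death itself is still captured by survival follow-up, so only its attribution is at risk.

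Footnote h's silence on late related AEs that are neither serious nor ECIs needs clarification and is not a second conflict. The day counts are spans of time, not shares of events. The documents give no rate of late events, so neither shortfall can be sized.

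**What to change.** 1. Amend the 12.4 sentence so that all SAEs and ECIs, related or not, are collected to 90 days after last dose or 30 days after new anticancer treatment starts, whichever is first, with only possibly related events afterwards. State which Safety Follow-up Visit is meant.
2. Add to footnote h that possibly related AEs of any seriousness starting after day 30 are recorded, as 12.4 already provides. The 12.4 criterion is possible relatedness, so no separate immune-mediated category is needed.
3. Put the same window and the same new-therapy anchor in Table 5, 8.3.15, 12.1.1 and 12.5. Section 12.5 must be included, because its open-ended rule would otherwise disagree with the amended 12.4 after day 90.

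Whether to keep Table 5's tracking of unrelated non-serious AEs on days 31 to 90 is the sponsor's choice. If it is kept, 12.4 and footnote h should say so.

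The cost is protocol wording and a few more eCRF entries at contacts already scheduled: the 8-weekly disease-assessment reviews in Table 4 and, for patients who progress, the 90-day safety contact in Table 5. Patients who start new therapy leave the 8-weekly assessments (Table 4 footnote b), so capture of their late related events will depend on the investigator learning of them, as it does now.

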While it is not currently possible to hypothesize the frequency or proportion of each mechanism, we believe that biopsies from participants prior to and during therapy will provide insight into purported mechanisms of failure or success to generate hypotheses that will provide the foundation for future study design.

Assessment of whether addition of ALKS 4230 can induce remission for patients with tumors that do not respond to anti-PD-1 treatment is the essential goal of the study. Understanding whether ALKS 4230 alters the number of NK cells and T cells within tumors is also critical. Thus, the post-treatment (second) biopsy will be collected during Week 2 (Cycle [C] 1, Day [D] 12 or at any time from C1D8 through C1D19).

The study population designates patients with advanced or recurrent HNSCC who are either refractory and progressive on prior anti-PD-(L)1 therapy or have failed to obtain response or tumor regression to anti-PD-1 therapy for more than 8 weeks to receive ALKS 4230 in combination with pembrolizumab. Patients in this population are as follows:

Group 1 (Cohorts 1 and 2) will consist of all patients with current SD (for at least 12 weeks) or partial response (PR) with no further reduction in tumor size or response for  $\geq 8$  weeks (ie, PR and not further improving).

Group 2 (Cohorts 3 and 4) will consist of patients with progressive disease (PD) with no prior response to anti-PD-(L)1 therapy after  $\geq 8$  weeks on anti-PD-(L)1 or current PD after prior achievement of a best response of SD or PR and after  $\geq 8$  weeks on anti-PD-(L)1 therapy.

HNSCC was chosen due to the high unmet need in this difficult-to-treat patient population with no effective therapeutic options for a number of reasons: 1) the demonstrated efficacy and recent approval of pembrolizumab for previously platinum-experienced recurrent or metastatic HNSCC, 2) the ease of serial biopsies in easily accessible sites of tumor in a proportion of patients, and 3) the responses to the combination of ALKS 4230 and pembrolizumab being

readily and easily assessable. However, if efficacy or response is observed, the combination could be tested in many different cancers.

This study will be performed in collaboration with the Immune Oncology Network (ION), who will perform activities related to, but not limited to, oversight and management of clinical sites, medical monitoring, and laboratory analysis services.

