- v The post-treatment (second) biopsy will be performed on the same or similar tumor site during the first cycle of therapy at C1D12, or at any time from C1D8 through C1D19.
- w Fecal swab/storage devices and instructions must be given to the patient; sample collection to be performed at home by patient and returned to clinical research site at the next study visit.
- x Additional information regarding correlative studies is located in Table 16, and additional instructions are provided in the Laboratory Manual.

Patient Group	Imaging	Follow-up	AE Tracking
Patients with SD/PR who continue on Tx, no progression, for up to 1 year	9 weeks post-treatment start (within 7 days prior to Cycle 4), then within 7 days prior to every 3 rd cycle Follow-up: every 12 weeks ±1 week	Safety Follow-up Visit at 30 days after discontinuation Clinic visit every 8 weeks	Until 90 days after discontinuation or 30 days after discontinuation if patient begins new anticancer therapy
Patients who progress on-study before 1 year	Per local standard of care	Safety Follow-up Visit at 30 days after discontinuation or before start of new therapy, if applicable (in- clinic) Safety Follow-up Visit at 90 days after discontinuation (in-clinic preferable, by phone possible) Survival telephone call every 12 weeks for up to 2 years	Until 90 days after discontinuation or 30 days after discontinuation if patient begins new anticancer therapy
Patients who discontinue treatment due to any reason other than progression	Per local standard of care or Investigator clinical judgment	Safety Follow-up Visit at 30 days after discontinuation or before start of new therapy, if applicable Clinic follow-up until toxicity resolves or until death	Until 90 days after discontinuation or 30 days after discontinuation if patient begins new anticancer therapy
Patients who achieve CR on Tx (after at least 24 weeks of Tx + 2 doses post-CR imaging)	After discontinuation of treatment: Follow-up: every 12 weeks ±1 week OR at clinical signs/symptoms of progression	Safety Follow-up Visit at 30 days after discontinuation Clinic visit every 8 weeks	Until 90 days after discontinuation or 30 days after discontinuation if patient begins new anticancer therapy

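### The coagulation row of the Table 4 grid shows no on-treatment test before the second biopsy, although footnote m to that row calls for one in all patients

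*Protocol*

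**What the plan says.** Three parts of Table 4 in Protocol 8.2 bear on this.

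- **Grid.** The row labelled "PT/INR and aPTT" carries two marks, one under screening and one under week 5. Weeks 1, 2 and 3 are blank.
- **Footnote m**, attached to that row, says the coagulation factors should be tested at screening and also "before collection of the post-treatment (second) biopsy for all patients". It adds closer monitoring throughout the study for patients on anticoagulants.
- **Footnote v** puts the second biopsy "during the first cycle of therapy at C1D12, or at any time from C1D8 through C1D19".

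The rest of the protocol agrees with footnote v. Section 5.2 says "the post-treatment (second) biopsy will be collected during Week 2" and gives the same day range, as do Sections 8.1 and 8.3.12.1. The biopsy row of the grid marks the second biopsy in week 2.

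Footnote j limits the screening laboratory tests to the 10 days before the first dose. Section 8.3.11 refers sites to Table 4 for the timing of laboratory samples.

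**The concern.** Footnote m asks for two tests: one at screening and one ahead of the second biopsy. The grid also shows two, but its second mark is in Cycle 2, after the biopsy window has closed. Footnote m names no week that would explain a week 5 test in all patients, and no other visible text does.

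The protocol itself links coagulation to biopsy safety: for patients on anticoagulants, Table 3 in Section 7.1 refers to a level judged safe for the planned biopsies. The second biopsy is mandatory unless it is bypassed for safety after discussion with the sponsor (Section 8.3.12.1). A visit worksheet or eCRF built from the grid alone would not prompt the pre-biopsy test. Sites that follow the footnote and sites that follow the grid would then handle the same procedure differently.

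There is also a possible small effect on the data. SAP 3.13.4 limits the laboratory summaries to scheduled collections, SAP 6.1 takes scheduled visits from the nominal eCRF visits, and SAP Table 1 includes PT (INR) and aPTT. If the eCRF has no slot for a pre-biopsy result, that result could be treated as unscheduled and left out of the by-visit tables.

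**Working it through.** No sample size, power or alpha figure is involved. The check is one of table position and calendar days.

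**1. Where the marks sit.** The week header of Table 4, as extracted, has 24 cells: a label, screening, weeks 1 to 18, end of treatment and three follow-up columns (1 + 1 + 18 + 1 + 3 = 24). The coagulation row also has 24 cells, with marks in cell 2 (screening) and cell 7 (week 5).

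Other rows read the same way also have 24 cells and land in plausible columns:

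| Row | On-treatment week marks |
|---|---|
| Pregnancy test | 1, 4, 7, 10, 13, 16 (cycle starts) |
| Adverse event review | 1, 2, 3, 4, then cycle starts |
| Biopsy | 1 (baseline), 2 (second) |
| PBMC immunophenotyping | 1 to 5, then cycle starts |
| PT/INR and aPTT | 5 only |

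A column shift confined to one row with a full cell count is unlikely, though only the original page can exclude it.

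**2. Weeks to days.** Week w covers study days 7(w − 1) + 1 to 7w. Footnote a states "Treatment cycles are 3 weeks", so week 5 is the second week of Cycle 2.

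- Week 2: Days 8 to 14
- Week 3: Days 15 to 21
- Week 5: Days 29 to 35
- Biopsy window: Days 8 to 19, that is, weeks 2 to 3

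**3. Gap from biopsy to the week 5 mark.**

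- Shortest: 29 − 19 = 10 days
- From the nominal biopsy day to the start of week 5: 29 − 12 = 17 days
- Longest: 35 − 8 = 27 days
- Shortest if the general −1 day visit window in footnote d is applied: 28 − 19 = 9 days

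A delayed Cycle 2 would lengthen the gap. No combination puts the week 5 test before the biopsy.

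**4. Age of the screening result at the biopsy.** If the test is done d days before Day 1, its age on Day b is d + (b − 1). Footnote j allows d up to 10.

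| Biopsy day | Test 1 day before first dose | Test 10 days before first dose |
|---|---|---|
| C1D8 | 1 + 7 = 8 days | 10 + 7 = 17 days |
| C1D12 | 1 + 11 = 12 days | 10 + 11 = 21 days |
| C1D19 | 1 + 18 = 19 days | 10 + 18 = 28 days |

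On the planned schedule, by C1D8 the patient has had one dose of pembrolizumab (Day 1) and five of ALKS 4230 (Days 1 to 5). The screening result reflects neither.

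**5. Side by side.** Footnote m asks for screening plus a test before a biopsy on Days 8 to 19. The grid shows screening plus a test on Days 29 to 35. The first items match and the second do not.

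**The case against.** The strongest case on the other side is that this is a clerical mismatch with little practical effect. Footnote m is explicit, covers all patients and hangs on the very row in question, so a site has to overlook it to miss the test. The grid gives less detail than its footnotes elsewhere: the ECG row is marked only at screening, week 1 and end of treatment, while footnote k asks for recordings on three days of every cycle. There are other safeguards too. Coagulation limits are part of eligibility, anticoagulated patients are watched more closely, biopsies follow site procedures, and the second biopsy may be bypassed for safety.

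Much of this stands, and it limits the size of the point. It does not remove it. In the ECG row the grid says less than the footnote. In the coagulation row it gives a week that the footnote does not mention and omits the time that it does. Section 8.3.11 sends sites to this same table, so the table has to agree with itself.

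A reader might go further in three ways that the documents do not support.

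- *Coagulation would be tested only after the biopsy.* The screening mark is in the same row and precedes the biopsy. What the grid lacks is the additional test that footnote m lists.
- *Week 5 is left over from a former biopsy date, since the second stool sample also falls there.* Footnote w covers only home collection of stool, nothing ties that sample to the biopsy, and two blood correlative rows are marked in week 5 as well.
- *Every patient with a second biopsy is affected.* That is the worst case. It would require all sites to follow the grid and disregard the footnote.

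**Conclusion.** The inconsistency is real and worth correcting before sites or the eCRF rely on the table. The grid shows no on-treatment coagulation test before the second biopsy, and its only on-treatment mark falls about 10 days or more after the last allowed biopsy day (9 if the visit window is used). The screening test offers partial cover. It can be up to 28 days old and predates both study drugs, and footnote m does not treat it as sufficient.

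The consequence is a possible omission at sites that work from the grid; the documents do not show that any test would in fact be missed. No endpoint, analysis population or statistical figure changes.

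The conclusion rests on the week 5 mark being where the extracted table puts it. Cell counts and neighbouring rows support that, but the original page has not been seen. Which timing should apply is a clinical matter for the sponsor.

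**What to change.** First check the original page of Table 4 for the position of the week 5 mark. If it is confirmed, reconcile the PT/INR and aPTT row with footnotes m and v so that grid and footnotes state the same timing relative to the second biopsy. If a week 5 test is also intended, say so and for whom. Then check that the eCRF visit structure matches the reconciled row.

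The cost is an edit to one table row or its footnote, plus the eCRF check. The sample size and the statistical analyses are not affected.
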